1 PROTOCOL SUMMARY

1.1 SYNOPSIS

Title:	A Team-Based and Technology-Driven Adherence Intervention to Improve Chronic Disease Outcomes
Study Description:	More than 50% of adults treated for diabetes, hypertension, or lipid disorders have suboptimal medication adherence, a prominent barrier to continued improvement in chronic disease care in the United States. Primary care providers (PCPs) often fail to identify medication nonadherence and/or have insufficient time and training to address underlying reasons for it. In this project, we propose a patient-centered and technology-driven strategy to identify patients with adherence issues and apply a team approach that will help them achieve evidence-based personalized goals for glucose, blood pressure (BP), or lipids. The study is a two-arm pragmatic patient randomized trial at 28 primary care clinics targeting adult patients not meeting recommended goals for BP, A1C, or statin use with poor medication adherence.
Objectives:	 (1) Identify and address nonadherence for adults with chronic diseases; (2) Improve management of previously uncontrolled blood pressure, blood sugar, and lipid disorders; and (3) Increase patient involvement in medication decision making.
Endpoints:	Primary Endpoint: (a) For each condition, achievement of an Epic generated proportion of days covered (e-PDC) \geq 80% for all medication classes for that particular condition (diabetes, hypertension, statin indication) in the 12 months following index date. (b) Mean change in systolic blood pressure (SBP) from the last BP within the 12 months prior to the index visit, to the last BP value within 12 months after the index visit. (c) Change in A1C value from the last lab test within 12 months prior to the index visit to the last lab test within 12 months prior to the index visit to the last lab test within 12 months prior to the index visit to the last lab

Study Population:	Secondary Endpoints: cost and cost effectiveness of the intervention. Tertiary Endpoints: (a) total 10-year American College of Cardiology/American Heart Association (ACC/AHA) Cardiovascular (CV) risk, (b) patient reported medication adherence using a validated survey instrument, (c) Patient and provider experience and satisfaction, (d) facilitators and barriers to implementation of the intervention The study includes adult patients from at least 28 HealthPartners Medical Group (HPMG) primary care clinics (HealthPartners (HP) and Park Nicollet (PN) in Minnesota.
Phase:	3

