The IMB conceptual model that guides this intervention (Figure below) posits that information is a prerequisite for changing behavior but by itself is insufficient to achieve behavior change.⁷³ Motivation is also a key determinant for behavior change and has been found to be a key factor in promoting adherence to chronic therapies, but the relationship between motivation and information constructs is elastic (a highly informed person may have low motivation and vice versa). Practically, the IMB model directs the pharmacist's attention to the influence of psychosocial factors related to adherence behaviors, including readiness to change, that evolve over time and cannot be addressed by information interventions alone. Interventions based on IMB have been effective at influencing behavioral change across a variety of clinical applications, including adherence to asthma medication and reduction of HIV risk behaviors.⁷⁴⁻⁷⁸ The IMB model incorporates elements of social cognitive theory (the importance of self-efficacy), stress coping model (dealing with the stress of the condition), and trans-theoretical model (incorporating readiness to change) – all of which are evidence-based and considered important for successful self-management interventions for people chronic disease.⁷⁹⁻⁸³ The IMB model has been endorsed by the WHO to address adherence problems, with recognition that the presence of both motivation and information increases the likelihood of adherence.^{28,84}

[figure not shown]

Figure 1: Information-Motivation-Behavior Change Framework

Experience with CDS Development and Implementation

We previously constructed and evaluated an EMR-based diabetes CDS system to improve outcomes in adults with type 2 diabetes in an NIH-funded clinical trial (DK068314). In a randomized trial of 11 clinics with 41 consenting PCPs and 2556 eligible diabetes patients we showed significantly better A1C (intervention effect -0.26%, 95% CI: -0.06 to -0.47, *P*=.014) and systolic BP (intervention effect -2.64 mm Hg, 95% CI: -0.19 to -5.10, *P*=.035) in intervention group than control group patients using a general linear mixed-model analysis with repeated time measurements and control for clustering. Low-density

Source: World Health Organization, 2003

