5 STUDY POPULATION

5.1 INCLUSION CRITERIA

To be eligible for the study, the patient must have an office visit with a clinician (physician or advanced practice provider) within a primary care department (family medicine, internal medicine, combined pediatric/internal medicine) at one of the 28 study clinics within the HealthPartners Medical Group or Park Nicollet care system, and meet all of the following criteria:

1. Age 18 to 75 years, inclusive. The evidence-based guidelines on which the CDS intervention is based are not applicable outside this age range.⁹¹

2. Have a primary care encounter (index visit) at a selected clinic.

3. Have a primary care encounter that meets one of or more of the following clinical criteria for care goals and medication adherence:

 In the 12 months prior to the index visit, most recent A1C ≥8% AND have one or more active non-insulin glycemic medications on their EMR medication list AND a potential adherence issue for one or more of these medications based on the Epic Medication Adherence score (e-PDC <80%, moderate or high confidence)

- Two consecutive encounters with BP values ≥140/90 mm Hg AND one or more BP medications on their EMR medication list AND a potential adherence issue identified (e-PDC <80%, moderate/high confidence)
- 3. Meet the ACC/AHA criteria listed below for moderate or high-intensity statin use AND a statin medication on their EMR medication list AND a potential statin adherence issue identified (e-PDC <80%, moderate/high confidence):
 - a. Age >21 with atherosclerotic CV disease identified by a CVD diagnosis on the problem list or two or more ICD-10 diagnostic codes in the last 2 years
 - b. Aged >21 and LDL >190 mg/dl
 - c. Aged 40 to 75 AND diabetes identified by the diagnosis on the problem list or two or more ICD-10 diagnostic codes in the last 2 years
 - d. Aged 40 to 75 with 10-year CV Risk Score 7.5% based on the ACC/AHA 10-year ASCVD risk equation.

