9.2 SAMPLE SIZE DETERMINATION

H1.1 (BP): Based on preliminary data collected in our study clinics between August 6, 2019 and December 23, 2019, we anticipate that 2,132 patients will meet study eligibility criteria of having at least one antihypertensive medication with e-PDC <80% over a 6-month enrollment period. For power analysis, we adjusted this estimate by half (N=1,066) to conservatively account for a potential continuation of the current decrease in office visit secondary to clinic, visit and provider changes as part of COVID-19 pandemic response. Further assuming a two-sided α =0.05, equal comparison groups (1:1 intervention/control), and a probability of outcome (adherence) in the control group of 50%, the analysis for H1.1a will have 80% power to detect a difference in the proportion of patients with 12month e-PDC ≥80% of 8.7% or more (e.g., 50.0% in control patients vs. 58.7% in intervention patients). For pre-post analyses of SBP outcomes, we estimate that to detect a clinically meaningful difference in mean 12-month SBP of 3 mmHg, assuming 80% power, α =0.05, SD=15.8, 1:1 intervention/control, and ρ =0.5 (correlation of repeated measures), a sample size of N=872 patients will be required. Given the projections described above (N=1,066), we expect sufficient enrollment to meet this target sample size.

H1.2 (Glycaemia): From preliminary data we estimate that 1,664 patients will meet study eligibility criteria due to having at least one non-insulin glucose medication with e-PDC <80% and having a most recent A1C \geq 8%. Adjusting this estimate by half (as above) we anticipate N=832. Assuming a two-sided α =0.05, equal comparison groups (1:1 intervention/control), and a probability of outcome (adherence) in the control group of 50%, the analysis for H1.2a will have 80% power to detect a difference in the proportion of patients with a 12-month e-PDC \geq 80% of 9.9% (e.g., 50.0% in control patients vs. 59.9% in intervention patients). For pre-post analyses of A1C outcomes, assuming α =0.05, SD=1.7, 1:1 intervention/control, and p=0.5 (correlation of repeated measures), and N=832, we expect 80% power to detect a clinically meaningful difference in A1C of 0.3% (e.g., 9.7% in control patients vs. 9.4% in intervention patients).

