The dependent variable in each model (antihypertensive medications, glucose-lowering medications, statins) is a binary indicator of high medication adherence (e-PDC \geq 80%) and is predicted by a binary indicator of adherence intervention assignment. We will screen and include patient characteristics in the model when they are unbalanced by treatment arm. In supplemental analyses, we will extend the GLM approach described above by including random intercepts to evaluate potential clustering effects at the level of clinic and/or provider.

H1 will be supported if the intervention group effect β_1 is significant and positive, supporting the prediction that clinical encounters with the adherence intervention are more effective than encounters without them for increasing medication adherence. Treatment group heterogeneity by patient sex, age group, race, insurance class, and comorbidity count will be assessed by including interaction terms consisting of products of patient variables and the intervention indicator.

Hypotheses H1.1b and H1.2b posit that patients assigned to the adherence intervention will be more likely than control patients to have reduced SBP (H1.1b) and reduced A1C (H1.2b) in the 12 months following the index visit.

 $E(Y)_t = \beta_{00} + \beta_{10}(Intervention) + \beta_{01}(Time) + \beta_{11}(Intervention * Time) + \beta_{c0}(Covariates)$ The analytic model will be a generalized linear model with an identity link and normal error distribution. The dependent variable Y (SBP for H1.1b and A1C for H1.2b) is predicted by a binary indicator of intervention assignment, time (pre-intervention vs. post), and the interaction of intervention assignment and time. We will screen and include patient characteristics in the model when

they are unbalanced by treatment arm, and will evaluate the potential for clustering by clinic and/or provider. A significant intervention group-by-time interaction term (P < 0.05) and a pre-specified contrast

A significant intervention group-by-time interaction term (*P*<0.05) and a pre-specified contrast indicating more reduction in SBP (H1.1b) or A1C (H1.2b) in the intervention than the control arm will support the prediction that encounters with the adherence intervention are more effective than encounters without it for improving BP and glycemic clinical outcomes.

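### The SBP and A1C change analysis (H1.1b, H1.2b) is valid but names no within-patient covariance; adjusting for the baseline already collected keeps or raises power at no cost

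*Combined protocol and SAP*

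**What the plan says.** The Synopsis (1.1) and the dependent-variable table in 9.4.2 define the SBP outcome as change: "Mean change in systolic blood pressure (SBP) from the last BP within the 12 months prior to the index visit", taken to the last value within 12 months after that visit. A1C is defined the same way.

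Section 9.4.2 models both the pre and the post value as responses. The predictors are arm, "time (pre-intervention vs. post), and the interaction of intervention assignment and time", plus patient characteristics found to be unbalanced. The model family is given in one sentence: "The analytic model will be a generalized linear model with an identity link and normal error distribution". Support for the hypothesis rests on the interaction at P<0.05. Clustering is mentioned for clinic and provider only.

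Other sections bear on the covariance. Section 9.2 uses a correlation of 0.5 for SBP ("correlation of repeated measures), a sample size of N=872 patients will be required") and again for A1C, where "we expect 80% power to detect a clinically meaningful difference in A1C of 0.3" percentage points at N=832. The Missing Data paragraph of 9.4.2 relies on direct likelihood under missing at random. Section 9.4.9 describes a mixed-model approach and says the primary analysis uses it too. Section 6.3 gives 1:1 allocation of individual patients.

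**The concern.** There are two separate gaps.

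1. **Covariance.** A pre/post model of two values per patient needs a statement of how those values are correlated. The power calculation and the missing-at-random argument both depend on it, and 9.4.2 does not write it down.

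2. **Efficiency.** The interaction test estimates a baseline arm difference that randomisation makes zero in expectation. Estimating it costs precision that baseline adjustment would recover. The plan's covariate rule does not do this, because it adds characteristics only when they are unbalanced and baseline is already a response in the model.

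H1.1b and H1.2b are two of the five primary tests, so even a modest gain is worth taking if it costs nothing.

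**Working it through.** **Inputs.** From 9.2: SBP difference 3 mmHg, SD 15.8, ρ=0.5, projected N=1,066; A1C difference 0.30, SD 1.7, ρ=0.5, N=832. Two-sided α=0.05. Let n=N/2 per arm and r = baseline SD / follow-up SD. The documents do not give r, so I assume 1.0, 0.8 and 0.6, and take the stated SD as the follow-up SD. Values of r below 1 are plausible because eligibility selects on baseline: "In the 12 months prior to the index visit, most recent A1C ≥8"% for A1C and "Two consecutive encounters with BP values ≥140/90 mm Hg" for BP.

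**Formulas.**
- Change: SE = SD·√[2(1+r²−2ρr)/n]
- Baseline-adjusted: SE = SD·√[2(1−ρ²)/n]
- Power = Φ(difference/SE − 1.96)
- Total N for 80% power = 4 × 7.849 × SD² × v / difference², where v is the bracketed variance factor

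**Reproducing the plan.** At r=1 and ρ=0.5, v=1 for change. Then 4 × 7.849 × 15.8² / 3² = 870.8, which is 436 per arm after rounding up, or 872. This matches the stated figure. For A1C at N=832, SE = 1.7·√(2/416) = 0.1179, and the difference detectable with 80% power is 2.80 × 0.1179 = 0.33, which rounds to the stated 0.3. At exactly 0.30 the power is Φ(2.545 − 1.96) = 72%.

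**Why adjustment cannot lose.** The difference between the two variance factors is (1+r²−2ρr) − (1−ρ²) = (r−ρ)². It is never negative, and it is zero only when r=ρ.

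**Power at ρ=0.5.**

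| Outcome | Change, r=1.0 | r=0.8 | r=0.6 | Adjusted |
|---|---|---|---|---|
| A1C 0.30, N=832 | 72% | 79% | 83% | 84% |
| SBP 3 mmHg, N=1,066 | 87% | 92% | 94.5% | 95% |

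The adjusted A1C SE is 1.7·√(2 × 0.75/416) = 0.1021, which gives Φ(2.938 − 1.96) = 84% and a detectable difference of 0.286. Before rounding, the gains are 11.5, 4.3 and 0.5 points for A1C and about 7.5, 2.5 and 0.3 points for SBP.

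**Sensitivity.**
- Section 9.2 does not say which SD 1.7 is. At r=0.8 the A1C comparison is 79 vs 84% if it is the follow-up SD, 72 vs 77% if the SD of change, and 60 vs 65% if the baseline SD.
- Over assumed ρ of 0.3 to 0.7 and r of 0.6 to 1.0, the gain is 0 to 18 points (A1C) and 0 to 16 points (SBP).
- N=832 and 1,066 are projections halved for COVID-19. At the unhalved N with r=1, A1C (1,664) is 95 vs 99% and SBP (2,132) is 99.2 vs 99.9%.

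**Type I error.** In simulation (6,000 replicates) change and ANCOVA both stayed near 5%, including when the baseline was truncated at its mean. Imposing a common baseline mean without the right covariance did not. With independent errors and the truncated baseline the simulated error was about 10%. With compound symmetry the formula gives 8% and 12% for assumed baseline SDs of 12 and 8 against a follow-up SD of 15.8.

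**The case against.** **The plan already meets its own targets.** N=872 reproduces, the A1C figure holds after rounding, the contrast matches the declared change endpoint, and N was deliberately halved. All of this stands. Nothing in the contrast is wrong, and the proposal is a more efficient estimator of the same effect.

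**The gain may be negligible.** This also stands in part. The 72 vs 84% comparison needs equal pre and post SDs, and selection on baseline makes that the favourable case. Holding ρ fixed while r moves is a simplification too, since selection would affect both. What remains is the direction: in large samples adjustment does not lose.

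**A common baseline does not supply the missing covariance.** Correct. Naming the within-patient covariance closes that gap, and the planned free-baseline model with an unstructured covariance would close it equally well. The two changes are separate.

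**A reader might infer that the plan will fit independent errors.** Taken literally, that fit at ρ=0.5 and equal SDs would have type I error of about 0.6% and power of 63% for SBP (N=1,066) and 41% for A1C (N=832). The documents do not support reading it as the intended analysis, because 9.2 assumes a correlation of repeated measures and the Missing Data paragraph invokes direct likelihood. The mixed-model wording in 9.4.7 and 9.4.9 is weaker evidence, since it could refer to clinic or provider effects. So is the team's earlier clinic-based trial, analysed by a "general linear mixed-model analysis with repeated time measurements and control for clustering" (Section 2.2).

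**A reader might want the 6-month values as a further row.** The outcome is the last value within 12 months, so a patient with only an early reading already has an outcome. With complete data the third row adds no power.

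**Conclusion.** The planned contrast is a valid change analysis whose within-patient covariance is implied but unwritten. Baseline adjustment is a free improvement. At ρ=0.5 and the planning N it adds from near zero to about 12 points of power for A1C 0.30 and to about 7 points for SBP 3 mmHg, with less to gain at the unhalved N. The direction is certain in large samples. The size is not, because it depends on an SD ratio and a correlation in a population selected on baseline, and the documents do not give the ratio.

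The result rests on the patient-level randomisation in 6.3. Section 10.1.9.1 still speaks of intervention and control clinics, but 4.2 explains that the clinic-randomised design was replaced.

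It would be too strong to conclude that the trial is underpowered for A1C: the shortfall at exactly 0.30 depends on equal SDs, on the halved N and on reading past the plan's rounding.

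**What to change.** In 9.4.2, replace the interaction test for H1.1b and H1.2b with ANCOVA: the last SBP or A1C within 12 months after the index visit, regressed on arm and the baseline value, two-sided α=0.05.

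An equivalent choice in large samples is a two-row (pre, post) likelihood model with a common baseline mean (no β₁₀ term), an arm effect at the post time only, and an unstructured within-patient covariance. This form sits most easily with the direct-likelihood wording under Missing Data. State the covariance explicitly. Do not drop the baseline arm term under independent errors or compound symmetry, because type I error can then exceed 5%.

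Name the same model in the Missing Data paragraph and in 9.4.9, so that the generalized linear model and mixed-model descriptions agree. No 6-month row is needed.

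The cost is SAP wording. Baseline is already extracted for the endpoint, and no patients, visits or alpha are added.

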9.4.3 ANALYSIS OF THE SECONDARY ENDPOINT(S)

Definition of Health Care Costs: Costs for this analysis include intervention costs and incremental medical care costs attributable to the intervention, defined from the health system perspective. Intervention costs include implementation, incentives to maintain high use rates, maintenance, and training but exclude research, development, and measurement costs.¹¹⁶ Standard micro-cost accounting methods and nationally representative pricing of inputs will be used to measure the cost of the intervention. We include clinic payments to reimburse pharmacist time and resources for conducting active outreach. Medical care costs include the cost of all prescribed medications and clinic services—including laboratory, MTM pharmacist, educator, and physician services—incurred in the 12-month preand post-index date periods by participants in each study group, as indicated by insurance claims and clinical encounter data. Emergency department visits and hospitalizations may be too infrequent in the study sample to accurately predict a population wide impact. To avoid substantially increasing variance without adding accuracy to the cost assessment, we will include emergency department and inpatient costs only if a significant difference in these is observed.

While market prices generally are a good estimate of the costs for medical services, the paid amount in this claims system is specific to HP at a particular time and may provide a biased view of costs between pre- and post-intervention periods. To address this, we will use Total Care Relative Resource Values[™]

(TCRRVs), which are a nationally standardized set of measures that have been endorsed by the National Quality Forum¹¹⁷ and are derived from Centers for Medicare and Medicaid Services (CMS) relative value units (RVUs). TCRRVs extend CMS RVU measures to include utilization categories, such as laboratory services and medications, which do not have CMS RVU weights¹¹⁸. Specifically, TCCRVs defined during the midpoint of patient accrual and follow-up (e.g., 2020) will be used to convert claims to represent U.S. dollars.

Analytic Plan for Health care costs (12-month Utilization): Incremental medical costs will be estimated using standard health econometric methods. A generalized estimating equation (typically assuming a gamma distribution and log link function) will be used to estimate costs by study arm while controlling for demographics and baseline clinical risk factors.¹¹⁹⁻¹²¹ The marginal effect of being assigned to an intervention clinic will provide an estimate of the incremental medical cost associated with the ReachOut adherence intervention.

Definition of Long-term Cost and Health Outcomes: Health outcomes include incidence, morbidity, and mortality of CV disease (including myocardial infarction, stroke, congestive heart failure, and angina pectoris) and microvascular complications due to diabetes (including blindness, ulcer, first amputation with no previous ulcer, first amputation with previous ulcer, second amputation, and renal failure). Medical costs corresponding with the incidence and ongoing management of these conditions are based on nationally representative data derived from the Medical Expenditure Panel Survey.¹²²

Analytic Plan for Long-term Costs and Outcomes: The HealthPartners Institute ModelHealthTM: A cardiovascular disease (CVD) microsimulation model will be used to estimate long-term outcomes and cost-effectiveness from the health system perspective.¹²³ ModelHealth: CVD is an annual-cycle microsimulation model that, in its base configuration, is parameterized to estimate lifetime CV events and disease costs in persons representative of the U.S. population. The model has been previously used to conduct a decision analysis for the U.S. Preventive Services Task Force recommendation on aspirin and to evaluate improvements in hypertension, lipid, and lifestyle management.¹²⁴⁻¹²⁹

The study population will be simulated at the patient level by assigning the known characteristics of the adherence intervention and control groups to synthetic counterparts. Age, sex, race/ethnicity, BMI, systolic BP, cholesterol, smoking status, CV disease history, diabetes status, A1C, and medication use for persons in each study group at the end of the study follow-up period will be entered into the model baseline. Linear, exponential, logarithmic and, if appropriate, polynomial trends, will be fit to the observed intervention differences in medication adherence, CV risk factors, and A1C (identified by H1.1-H.3 and secondary analyses) and used to project future differential trends between the simulated ReachOut adherence intervention and control groups. Incidence of major CV events will be determined using risk equations developed specifically for the model using Framingham Heart Study data.^{130,131} Calculation and reporting of incremental cost-effectiveness ratios (ICERs) will follow the guidelines of the Panel on Cost-Effectiveness in Health and Medicine.¹³² ICERs will be estimated with a 30-year analytic horizon in the primary analysis, and 10- and 20-year horizons will be considered in secondary analyses. Sources of uncertainty will be evaluated using standard sensitivity methods.¹³³

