4.2 SCIENTIFIC RATIONALE FOR STUDY DESIGN

This trial was originally conceived and approved as a clinic cluster randomized trial of control (usual care) versus intervention. However, the intervention was suspended in March 2020 after one week of implementation due to COVID-19 pandemic response that resulted in loss of the separation of treatment groups. There were clinic closures, decreased office visits, and increase in telehealth care. To address concerns related to patient crossover from intervention to control settings (and vice versa) in the ongoing COVID-19 era, the study was transitioned to a patient level randomization that was conducted using a computerized allocation by the CDS at the time of an index visit within any of the 28 study clinics. The main advantage to the patient level randomization is that no matter what happens with clinics closing and opening, provider moving between clinics, and where video encounters take place, the study subjects consistently receive the ReachOut intervention or usual care without crossover. Additionally study power increases with the patient-level design compared to a clinicrandomized design. The disadvantage to the patient level randomization design, and why it wasn't the initial choice when the grant was originally funded, is concern over clinician contamination due to a potential learning effect from the intervention that translates to control patients. However, the net effect of this contamination would be a reduction in the intervention effect which would not undermine conclusions if the intervention is found to be effective. Given how the clinical setting changed abruptly and unexpectedly due to the COVID-19 pandemic, the advantages of a patient-level study design were determined to outweigh the disadvantages and be the most appropriate way to complete the study and test the hypotheses.

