6.1 STUDY INTERVENTION(S) ADMINISTRATION

6.1.1 STUDY INTERVENTION DESCRIPTION

Control: All control patients will continue to receive the basic EMR-linked CDS for management of CV risk factors and other chronic conditions. This CDS has been described in detail in previous publications, and includes algorithmically derived identification of high CV risk patients and prioritized treatment suggestions for lipids, BP, glycemic control, weight, tobacco, and aspirin use based on distance from goal, current medications, labs, allergies, and safety considerations.^{85,92-97} The basic CDS does not include information on medication adherence.

Intervention: For intervention patients, the basic CDS system for CV risk-factor control is enhanced to support a team-based care model that identifies risk of nonadherence, incorporates medication adherence information into the CDS, creates a registry to direct proactive pharmacist outreach, and coordinates action plans (Figure below).

Figure 2: Operational Model for Adherence Intervention

To do this, the CDS Web service will combine EMR-identified medications with e-PDC data. Algorithms will identify poor adherence using e-PDC scores available within the Epic EMR at patient encounters. When medication adherence issues are identified, alert messages will appear on the CDS tools for patients and providers. Patients with index visits will be followed-up for 6 months as they continue to receive CDS at subsequent encounters. At 6 months, patient e-PDC as well as clinical outcomes will be reevaluated.

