6.4 STUDY INTERVENTION COMPLIANCE

Training

Intervention pharmacists will be compensated to attend a 2-3-hour training session to learn the IMB framework, modules related to the chronic diseases addressed, interviewing techniques, and how to use the registry and EMR tools for tracking outreach attempts and documentation. All training will be conducted collaboratively with Goodrich, HealthPartners and Park Nicollet pharmacy directors and managers and the research team. The training format will be modeled after successful pharmacist training programs previously conducted in our care system by pharmacy leadership for diabetes. Training materials will include written materials with companion online and Web-based modules related to the diseases addressed and the IMB intervention. Targeted individual follow-up training may be provided as needed. For PCPs and clinic staff, we will conduct luncheon training sessions (providers, nurses, pharmacists, and rooming staff) either in-person or through webinars that focus on workflow and enhancements to the basic CDS system to address medication adherence. We will also send information through newsletters and communication via email to clinic leaders through the care system leadership.

Follow-up

Rates of PCP use of the CDS and rates of completed pharmacist outreach will be monitored continuously during the study period (through electronic reports) and reported monthly to clinic and pharmacy leadership. If needed to increase use rates and consistent with our previous successful CDS implementation, small incentives (e.g. \$250 per clinic semi-annually) may be provided to clinics whose PCPs achieve CDS use rates at >75% of eligible encounters in both intervention and control sites.

The outreach, including the percent of patients with completed outreach contact will also be tracked. Per agreement with the participating pharmacies, we will provide compensation for time spent implementing the outreach. If necessary, trouble shooting with pharmacy leaders and/or supplemental training will be provided to pharmacists with low completed contact rates. While the proposed intervention is rooted in the pragmatism of the current health care world, it is also based on an established process-control conceptual model, current theories of behavior change, and our previous work on chronic disease prevention and control in the study population.¹⁰⁴⁻¹⁰⁶ Study Team Monitoring

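### CDS-use incentives are listed as an intervention cost but offered for both arms, so incremental cost may be slightly overstated if they are paid

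*Combined protocol and SAP*

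**What the plan says.** Section 9.4.3 (definition of health care costs) builds the analysed cost from two parts: intervention costs, and incremental medical care costs attributable to the intervention. On the first part it says "Intervention costs include implementation, incentives to maintain high use rates, maintenance, and training", and it leaves out research, development and measurement costs. It names no corresponding cost for the control arm and no step that nets out costs common to both arms.

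Section 6.4 (follow-up) describes the incentives. They are conditional: "If needed to increase use rates and consistent with our previous successful CDS implementation". The amount is modest, with $250 for each clinic every half-year given as the example. On who can receive the money, the section says it "may be provided to clinics whose PCPs achieve CDS use rates at >75% of eligible encounters in both intervention and control sites".

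Section 6.1.1 says of the comparator: "All control patients will continue to receive the basic EMR-linked CDS for management of CV risk factors and other chronic conditions". ReachOut adds adherence information, a registry, pharmacist outreach and coordinated action plans to that CDS.

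Section 4.2 explains the move from clinic to patient randomization, with allocation made "at the time of an index visit within any of the 28 study clinics". Section 6.3 gives the ratio as 1:1.

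**The concern.** An incremental cost should contain only what ReachOut adds to the care that controls receive. A payment offered on the same terms for CDS use in both arms is not such a cost. Read literally, 9.4.3 places it on the intervention side, and nothing on the control side offsets it.

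The redesign sharpens the problem. When clinics were randomized, a per-clinic payment belonged to one arm. Now a clinic can hold patients of both arms, so the payment needs an allocation rule, and none is given. The cost text was not fully updated: 6.4 still speaks of sites by arm, and the analytic plan for 12-month costs in 9.4.3 still describes the marginal effect as that of allocation to a clinic.

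Cost and cost-effectiveness are the secondary endpoint, and Section 3 says the delivery cost is meant to inform adoption elsewhere. Charging a shared cost to one arm would push the incremental cost up, against the intervention.

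**Working it through.** The documents state no intervention cost, incremental cost or cost-effectiveness ratio, so there is no figure to reproduce. The check is an upper bound on the amount that could be charged wrongly.

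**Inputs**
- Clinics: 28 (Section 4.2).
- Payment: $250 per clinic per half-year, given as an example (Section 6.4).
- Duration: 12 months, the horizon of Hypothesis 2.1 (Section 9.1), and 18 months, the minimum intervention duration (Section 4.1). These are 2 and 3 half-years.
- Projected cohorts (Section 9.2): blood pressure 2,132, glycaemia 1,664, statin 3,388. Each is halved there for the pandemic to 1,066, 832 and 1,694.
- Allocation: 1:1 (Section 6.3).

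**Maximum payment** = clinics × payment × half-years
- 12 months: 28 × 250 × 2 = $14,000
- 18 months: 28 × 250 × 3 = $21,000

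**Intervention patients** = total N / 2. A patient may qualify under more than one condition and the overlap is not given, so N runs from the sum of the cohorts (no overlap) down to the largest cohort alone (complete overlap).
- Halved, no overlap: (1,066 + 832 + 1,694) / 2 = 3,592 / 2 = 1,796
- Halved, complete overlap: 1,694 / 2 = 847
- Unhalved, no overlap: (2,132 + 1,664 + 3,388) / 2 = 7,184 / 2 = 3,592
- Unhalved, complete overlap: 3,388 / 2 = 1,694

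**Cost per intervention patient if charged in full** = maximum payment / intervention patients

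| Enrolment | 12 months | 18 months |
|---|---|---|
| Halved, no overlap | 14,000 / 1,796 = $7.80 | 21,000 / 1,796 = $11.69 |
| Halved, complete overlap | 14,000 / 847 = $16.53 | 21,000 / 847 = $24.79 |
| Unhalved, no overlap | 14,000 / 3,592 = $3.90 | 21,000 / 3,592 = $5.85 |
| Unhalved, complete overlap | 14,000 / 1,694 = $8.26 | 21,000 / 1,694 = $12.40 |

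If the payment splits 50:50 by arm and only the control half is excess, each entry halves. Over 12 months the range becomes $3.90 to $8.26 with halved enrolment and $1.95 to $4.13 unhalved. If no incentive is paid, every entry is zero.

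**The case against.** The strongest reply is that the plan lists cost categories and does not say that control-side incentives go to the intervention. Three parts of it stand.

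- **Payment is conditional.** The scheme depends on need and the amount is an example. Section 2.2 reports that clinicians already use this CDS at more than 75% of targeted visits, so the scheme may never be started.
- **The framing is incremental.** Section 3 measures the cost of delivering the intervention, and 6.1.1 defines the intervention as an enhancement of the basic CDS. A careful analyst could net out shared costs without being told to.
- **The payment rule dates from the clinic-randomized design.** The schedule of activities describes the prompt to print CDS tools for the intervention-assigned patient, so the rewarded use might mainly concern intervention encounters. The documents do not settle this.

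There is also a case for counting some incentive cost, because a system adopting ReachOut may have to pay to sustain use.

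A reader might go further and infer that maintenance of the basic CDS is also charged to ReachOut. The text does not show this: maintenance in 9.4.3 can equally mean maintenance of the enhancement.

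None of this reconciles 6.4 with 9.4.3. One offers the incentive for both arms; the other lists it as an intervention cost without limiting it to the intervention share.

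**Conclusion.** The two sections do not fit together, and 9.4.3 followed literally charges a shared cost to one arm. If incentives are paid and charged in full, the intervention cost and the incremental cost are overstated by at most about $8 to $17 per intervention patient over 12 months with halved enrolment (about $4 to $8 unhalved). Over 18 months the figures are about $12 to $25 (about $6 to $12 unhalved). These are upper bounds: they assume that every clinic earns every payment at the example amount, and their width reflects unknown cohort overlap.

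A reader might infer that the cost and the cost-effectiveness ratio are in fact overstated. The documents do not support that. They do not say that any incentive will be paid, and they are silent on how one would be allocated. The effect on the ratio cannot be computed, because neither a total cost nor a health gain is given. A higher incremental cost would raise the ratio only if the health effect is positive; if the intervention saves money, it would reduce the net saving instead. This is a minor point, worth settling before costs are tallied.

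**What to change.** In 9.4.3:
- State that intervention costs are only those incremental to the basic CDS that control patients receive.
- Charge CDS-use incentives offered for both arms equally to both, so that they cancel. Count an incentive as an intervention cost only where it is paid for intervention encounters alone.
- Keep the existing exclusion of research, development and measurement costs.

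In 6.4 and in the 12-month cost model of 9.4.3, replace the wording that assigns sites or clinics to an arm with wording that matches patient randomization.

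The change takes a few sentences and no new data. The reported intervention cost may come out slightly lower. A system that would newly have to pay incentives in order to adopt the CDS would need to add them back; a sensitivity analysis that includes the incentives can show that figure.
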